Early Intervention to Reduce Alcohol Misuse and Abuse in the Ohio Army National Guard
(Project GUARD)

Protocol

Version Date: 02/18/2019

NCT Number: NCT02860442

Objectives

The proposed project, Project GUARD, is a fully-powered randomized controlled trial of a smartphone app which includes an alcohol brief intervention (SP-BI) versus an Enhanced Usual Care (EUC) condition for National Guard members in the State of Ohio who meet criteria for at-risk drinking in the previous 4 months.

The specific aims are to compare SP-BI and EUC in:

1. Reducing the frequency and intensity of at-risk drinking at 4-, 8- and 12-months;
2. Decreasing binge drinking at 4-, 8- and 12 months.

The secondary aims are to:

1. Compare the SP-BI and EUC conditions in reducing the frequency of illicit drug use and depressive symptoms at 4-, 8- and 12-months;
2. Examine if deployment status moderates the effect of intervention assignment (SP-BI or EUC) on post-intervention drinking, depressed feelings, and other substance use.

Design

After tailoring the content of the SP-BI intervention for NG soldiers, the proposed study will screen ~3,100 individuals over the three year enrollment period to identify 750 participants with at-risk drinking across the 2 sites. Participants in this study will be randomized to either the SP-BI (n=375) or the EUC condition (n=375) and followed at 4, 8 and 12 months post-enrollment. The study is intended to address the primary and secondary aims and corresponding hypotheses listed below.

Methods

Participants who are randomized to the SP-BI condition will receive an informational brochure with resources available to members of the military related to mental health and alcohol use and will download a free app on to their smartphones. The app will be developed to be used on both Android and iPhone platforms and will be used over 12 weeks to deliver the study intervention. They will be contacted to complete 4-, 8-, and 12-month follow-up assessments.

Those assigned to the control condition will receive an informational brochure with resources available to members of the military related to mental health and alcohol use. They will be contacted to complete 4-, 8-, and 12-month follow-up assessments.

Randomization:

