In general, for longitudinal analysis we will use repeated measures regression mixed effects models for continuous and non-normally distributed variables. We will use procedures SAS PROC MIXED for continuous variables and PROC GLIMMIX for dichotomous and count data (either Poisson or negative binomial), both of which allow for subject-specific inference (e.g., allows for the estimation of subject-specific effects of interventions). The selection of the covariance matrix in the PROC MIXED procedure will be determined by the distribution of the data (e.g., normally) and covariance structure. The random parameter specified will be the subject effect and we will test for random slopes and intercepts. One of the advantages of these analytic approaches is that all available data are used in the analysis, rather than case-wise

deletion if a follow-up interview is missing (see below for more detail). All analyses of the intervention and EUC condition will adjust for the two randomization stratification variables, gender and diagnosis of alcohol use disorder.

Missing data. To minimize missing data, we will make every effort to gather follow-up information for all participants. Specific strategies to retain participants that have proven successful in our prior research are described above. The use of mixed effects regression to model individual trajectories will allow the use of data from all participants (including those with incomplete follow-up data) and provides unbiased parameter estimates that account for missing data under the missing-at-random assumption.¹⁴⁸ If our examination of the pattern of missingness suggests that the missing-at-random assumption is untenable, we will handle missing data with a pattern mixture model.¹⁴⁹ Where we have missing data on individual variables that are necessary for analysis, we will impute using SAS PROC MI to perform multiple imputation of missing data and PROC MIANALYZE to combine the results of PROC MI. We have found that sometimes 5 imputations are not enough to achieve optimum results and we increase number of imputations until we see each variable having 100 degrees of freedom or more.

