Power Analyses. We propose to enroll a relatively large N at baseline (750, or 375/baseline group) in order to have sufficient power to: (1) detect potentially smaller differences in outcomes of SP-BI compared to EUC as SP-BI has potential for successful implementation even if effect sizes are smaller because of the relatively low cost to maintain this technology-based intervention, and (2) have sufficient power for tests of moderators of the interventions. Longitudinal mixed effects models for binomial, count, and continuous dependent variables will be used to test the aims. We estimate power for an anticipated reduced sample size at 12 months assuming a conservative 80% follow-up (achieved in our previous studies with this population), even though our proposed mixed models use all available follow-up data.

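### PROC GLIMMIX is named without an estimation method; at its default pseudo-likelihood, binary-outcome effects would be attenuated and the missing-at-random statement would not carry over

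*Combined protocol and SAP*

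**What the plan says.** In the longitudinal-analysis paragraph of the SAP, continuous outcomes go to PROC MIXED and the rest to "PROC GLIMMIX for dichotomous and count data". The plan describes the two procedures as "both of which allow for subject-specific inference". The random part is given as "The random parameter specified will be the subject effect and we will test for random slopes and intercepts". No sentence anywhere names quadrature, Laplace or pseudo-likelihood, and no random-effect variance is given.

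The Missing data paragraph then says of mixed-effects regression that it "provides unbiased parameter estimates that account for missing data under the missing-at-random assumption". This makes no distinction between the two procedures. A pattern mixture model is held in reserve, but only if missing at random looks untenable.

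Participants are "followed at 4, 8 and 12 months post-enrollment", so there are three follow-up observations per person. Whether baseline enters as a fourth repeated measure is not stated. Power Analyses confirms that binomial models are among those that will test the aims, and plans for loss by "assuming a conservative 80% follow-up" at 12 months.

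**The concern.** PROC MIXED maximises a (restricted) likelihood. PROC GLIMMIX with random effects and no METHOD= option does not: it linearises the model, fits a weighted linear mixed model to a pseudo-response, and iterates. That default is a property of the named software, not something the documents state. Two consequences follow for binary data.

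First, the linearisation is poor when each person contributes few binary observations. The random-effect variance is underestimated and the subject-specific log odds ratio is pulled toward zero.

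Secondly, the protection under missing at random comes from using the true likelihood of the observed data. A pseudo-likelihood fit does not use it, so the sentence in Missing data is not supported for that fit. The pattern mixture fallback would not catch this, because it is triggered by doubt about the missing-data assumption and not by the estimator.

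At stake are the reported size of any binary effect, its interval, and a robustness claim made in a trial that plans for 20% loss.

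**Working it through.** The plan gives no figure to reproduce, so the check is by simulation.

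**Inputs from the documents.** 375 per arm; three visits (4, 8 and 12 months); 80% follow-up at 12 months, i.e. 375 × 0.80 = 300 per arm.

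**Assumptions (not in the documents).** Random-intercept logistic model, logit P(y = 1) = b0 + effect × arm + u, with u normal with standard deviation SD; true subject-specific log odds ratio −0.6; SD from 0.75 to 3. The latent intraclass correlation is SD² / (SD² + π²/3). For example, at SD 2 it is 4 / (4 + 3.29) = 0.55.

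**Step 1: attenuation, complete data.** 750 participants, 150 replicates per cell, prevalence about 58% to 64% in the cells shown. Each data set was fitted by residual pseudo-likelihood and by maximum likelihood with 30-point quadrature. Entries are mean absolute log odds ratios.

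| SD | Latent ICC | Pseudo-likelihood | Quadrature | Ratio | Attenuation |
|---|---|---|---|---|---|
| 1.0 | 0.23 | 0.530 | 0.619 | 0.86 | 14% |
| 1.5 | 0.41 | 0.455 | 0.592 | 0.77 | 23% |
| 2.0 | 0.55 | 0.412 | 0.597 | 0.69 | 31% |
| 2.5 | 0.66 | 0.380 | 0.606 | 0.63 | 37% |
| 3.0 | 0.73 | 0.362 | 0.635 | 0.57 | 43% |

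At SD 0.75 (ICC 0.15) the attenuation is about 10%. A separately coded simulation (300 per arm, true odds ratio 0.60, 120 runs per cell) gave ratios of 0.855, 0.769 and 0.691 at SD 1, 1.5 and 2. On that scale, exp(ratio × ln 0.60) with ln 0.60 = −0.511 gives 0.65, 0.68 and 0.70 in place of 0.60.

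**Step 2: effect on the test, complete data.** Rejection rates by pseudo-likelihood and quadrature were 0.96 and 0.96 at SD 1.5, 0.91 and 0.91 at SD 2, and 0.68 and 0.65 at SD 3. The standard error shrinks along with the estimate.

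**Step 3: dropout at random.** With 18% to 23% missing at 12 months, attenuation of the overall effect relative to quadrature was 13–14%, 21% and 27–28% at SD 1, 1.5 and 2.

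A harder case used an arm-by-visit model, dropout depending on arm and on the last observed outcome (76% to 79% observed at 12 months), and 250 replicates. With a true 12-month effect of zero:

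| SD | Pseudo-likelihood | Quadrature | Difference | Pseudo-likelihood rejection at 5% |
|---|---|---|---|---|
| 1.0 | −0.046 | +0.013 | −0.059 | 6% |
| 1.5 | −0.065 | +0.045 | −0.110 | 5% |
| 2.0 | −0.169 | −0.036 | −0.133 | 12% |

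Monte Carlo standard errors are 0.012 to 0.017. The quadrature means are not all within two of these of zero, but they have no consistent sign, so the within-data-set difference is the figure to read. With complete data both methods lay between −0.02 and 0.00. With a true effect of −0.6 and the same dropout, pseudo-likelihood gave −0.584, −0.550 and −0.562 against −0.621, −0.594 and −0.616 by quadrature. There the dropout shift partly offset the attenuation, so the net direction of error depends on who drops out.

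**Step 4: counts.** Poisson random-intercept model, true log rate ratio −0.30, SD 0.7 and 1.0, 60 replicates. Shrinkage was about 1% at conditional means of 10 and 20, 7% at mean 4 with SD 0.7 (the SD 1.0 cell did not converge), and 3% and 11% at mean 1.

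**The case against.** The strongest reply is that silence is not a choice. A reader might infer that the plan has adopted pseudo-likelihood. It has not: GLIMMIX can also fit by likelihood, and the SAP describes itself as an outline. That stands, and the conclusion is therefore conditional on the default being run. But the text followed literally leads to the default, and the SAP claims a property that the default lacks, so this is more than missing detail.

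A reader might also infer that odds ratios for binge drinking are at risk. The documents do not support this. The Alcohol Use paragraph under Measures says that exact numbers will be obtained and that the consumption variables, binge drinking among them, will be analysed as counts or on continuous scales. The PHQ-9 is a 0–27 score, and the drug-use aim concerns frequency. No aim outcome is assigned a binary scale. Binary models remain planned in general terms in both the longitudinal-analysis and Power Analyses paragraphs, and the SAP allows categories to be collapsed, so the point is live but attached to no named outcome.

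Three further limits stand. Tests with complete data hardly change. The missing-at-random shift was shown under deliberately strong dropout that differed by arm. And although pseudo-likelihood fits give no comparable likelihood for choosing between Poisson and negative binomial, the plan does not say that it will choose that way, so nothing rests on this.

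**Conclusion.** The point holds conditionally. If GLIMMIX is run at its default, subject-specific log odds ratios for any binary outcome with three follow-ups would be attenuated by about 15% to 31% for a random-intercept SD of 1 to 2, and about 10% to 43% for SD 0.75 to 3. The SD is an assumption, so neither range is a property of the plan. The missing-at-random sentence would not carry over to such a fit. The size of that departure depends on the dropout pattern: the differences from quadrature of 0.06 to 0.13 on the log-odds scale belong to a severe pattern.

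The harm is to effect estimates and intervals. It would go too far to say that the trial loses power or that its alcohol consumption results are compromised: counts are little affected unless their means are low. Including baseline as a fourth repeated measure was checked only at SD 0.75, where attenuation was about 9%. Negative binomial models were not simulated.

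**What to change.** Add to the GLIMMIX sentence: *dichotomous and low-count outcomes will be fitted by maximum likelihood using METHOD=QUAD (adaptive quadrature), or METHOD=LAPLACE if more than one random effect makes quadrature impractical, and not by pseudo-likelihood.* The missing-at-random sentence then rests on a likelihood for these outcomes as well. In the three-visit simulations, quadrature gave mean log odds ratios of 0.58 to 0.64 against a true 0.60, and it removed most of the shift under dropout.

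The cost is one SAS option and longer run time, which is minor with 750 participants and one random effect. One reservation: the plan will test random slopes, which could lead to the Laplace branch, and Laplace was not checked here for three binary visits.

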After the baseline assessment is completed, participants will be assigned to one of the two study conditions (SP-BI or EUC) using a computerized randomization system. Random assignment will be stratified based on gender and an AUDIT- \geq score > 19 .

Intervention

Brief Intervention

Smart Phone (SP-BI) Content. Participants in the SP-BI condition will receive a 20-30 minute intervention session through an app program. The intervention will be based on the FRAMES

format: providing personalized Feedback (regarding substance use, risk factors), emphasis on Responsibility for change, Advice, Menu of options, Empathic clinical behaviors, and support of Self-efficacy regarding making changes. The intervention is designed to address the primary target behavior of alcohol use, and will include a tailored review of participants' goals/values, feedback regarding their present alcohol use patterns and consequences (either actual experiences or potential based on risk behaviors), developing a discrepancy between their alcohol use and ability to meet goals and values through a decisional balance exercise, and formulation of a "change plan" tailored for each participant.

Measures

Background Characteristics. The Substance Abuse Outcomes Module (SAOM) will be used to measure background characteristics including basic demographics (i.e., gender, age, race, ethnicity, marital status) and other background variables (e.g., education, employment, income, legal history). The SAOM has undergone extensive reliability and validity examinations (Smith et al., 2006).

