Readiness to Change. We will also have additional questions related to the importance and confidence to change as separate components of readiness to change. We will measure with the use of visual analog rulers; these rulers have been shown to correlate with longer surveys, and to predict outcomes in alcohol intervention studies (Daepfen et al., 2007; Hesse, 2006; LaBrie et al., 2005).

Social Support. Social support will be assessed using the Deployment Risk and Resilience Inventory (DRRI) (King et al., 2006). The DRRI survey instrument is used to assess the key deployment-related factors implicated in the health and well-being of military veterans. With the nature of military deployment changing, with a larger proportion of women, National Guard and Reserves being deployed for more contemporary conflicts, the DRRI was developed to provide a more comprehensive assessment of the current combat-related experiences.

Alcohol-related consequences. The Young Adult Alcohol Consequences Questionnaire (Barry et al., 2012; Kahler et al., 2005; Tripp et al., 2015) will be used to measure consequences of alcohol

use. This measure has been used in the National Guard population.

Barrett Impulsiveness scale. Measures impulsive behaviors including behaviors related to motor control, non-planning, attention, internal stimulation, & external motivation (Patten et al., 1995).

The Conflict Tactics Scales (CTS). The Conflict Tactic Scales (Straus, 1990) is the most widely used measure of domestic violence. We will use a collapsed version of the CTS to measure partner and non-partner violence.

Dimensions of Anger Reactions. The DAR measures anger disposition directed towards others primarily measures Trait Anger. The DAR is a psychometrically strong measure, potentially useful for the evaluation of anger in PTSD (Forbes et al., 2004; Novaco & Chemtob, 2002).

Post-app assessment. The post-intervention assessment will include questions regarding importance and usefulness of the app will occur following the 12 week SP-BI.

Statistical Analysis Plan (SAP)

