To minimize the likelihood of chance associations (i.e., protect against Type I errors) which can occur when multiple, unplanned analyses are conducted with large data sets, analyses for testing the main study hypotheses will be planned a priori, and will be limited to the examination of specific outcomes. In addition, analyses that are central to the purpose of the study will be clearly identified as confirmatory hypotheses, and will be clearly identified as separate from exploratory analyses. This plan of analyses is intended to outline the primary data analytic approaches that will be used to test the hypotheses for the specific aims. We will utilize an “intent-to-treat” approach in all analyses to be conservative in our estimate of intervention effects.

It is our standard practice to begin with descriptive data analyses to determine distributions of key variables, calculate transformations or collapse categories, if necessary, and review data for outliers and anomalies. Tests for linearity, independence, missingness, and distributional assumptions (e.g., normality) will also be performed. Normalizing transformations of the dependent variables will be utilized when appropriate. We will validate the randomization scheme by comparing the initial groups on key variables that could be associated with the outcomes, such as age, race, initial alcohol use severity, comorbidity, self-efficacy and stage of change. Stratified randomization should equalize the intervention groups on the key variables of gender and diagnosis of alcohol use disorder. Where we identify significant differences between groups, we will either adjust for these variables in analysis.

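### Does the claim of sufficient power for moderator tests need revising because deployment status and its interaction term are not spelled out?

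*Combined protocol and SAP*

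**What the plan says.** Under Objectives, secondary aim 2 is to "Examine if deployment status moderates the effect of intervention assignment (SP-BI or EUC) on post-intervention drinking, depressed feelings, and other substance use". Under Design, participants are "followed at 4, 8 and 12 months post-enrollment".

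The Measures section goes instrument by instrument. Background Characteristics covers basic demographics and "other background variables (e.g., education, employment, income, legal history"), a list given by way of example. The one instrument with deployment in its name has another job: "Social support will be assessed using the Deployment Risk and Resilience Inventory (DRRI").

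The SAP says that confirmatory analyses "will be clearly identified as separate from exploratory analyses". For the models it states: "All analyses of the intervention and EUC condition will adjust for the two randomization stratification variables, gender and diagnosis of alcohol use disorder". On random effects it says "we will test for random slopes and intercepts". Baseline variables that differ between groups may also be adjusted for.

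Power Analyses gives two reasons for the sample size: to detect possibly small differences between SP-BI and EUC, and to "have sufficient power for tests of moderators of the interventions". It assigns longitudinal mixed models to the aims as a whole and bases power on 80% follow-up at 12 months. It gives no alpha, power value, effect size or interaction size.

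**The concern.** A claim of sufficient power needs a defined test to refer to, and here the test has to be inferred. Deployment status could mean ever deployed, deployed recently before baseline, or deployed during the 12 months of follow-up. These are different variables. The third is observed after randomization, so an interaction with it is not a baseline moderator effect. The SAP does not mention deployment, writes out no interaction, and does not say whether aim 2 is confirmatory or exploratory. Power Analyses also speaks of moderators in the plural, while the aims name one.

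An analyst might therefore choose a coding with the data in hand. Moderation present under one coding could be missed under another, or several codings could be tried and the favourable one reported. Aim 2 spans three outcome domains, so the choice would arise more than once. Moderator power is also part of the argument for N = 750, so an empty claim there would weaken the sample-size justification.

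**Working it through.** **Inputs from the documents.** N = 750, 375 per arm (Design; Power Analyses). Follow-up at 12 months is 80% (Power Analyses).

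**The plan's own figures.** 750 × 0.80 = 600, and 375 × 0.80 = 300 per arm. This is consistent. The power statement itself cannot be reproduced, because alpha, power, effect size and SD or event rates are not given.

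**Assumptions, not in the documents.** Two-sided alpha 0.05, 80% power (1.960 + 0.842 = 2.802), continuous outcome with SD 1, one comparison at 12 months, binary deployment variable with share deployed p from 10% to 50%.

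**Detectable main effect.** 2.802 × √(2/300) = 2.802 × 0.0816 = 0.23 SD.

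**Detectable interaction.** The standard error is 2/√(600·p(1−p)).

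| Share deployed | SE | Detectable interaction | Ratio to main effect |
|---|---|---|---|
| 50% | 0.163 | 0.46 SD | 2.0 |
| 30% | 0.178 | 0.50 SD | 2.2 |
| 20% | 0.204 | 0.57 SD | 2.5 |
| 10% | 0.272 | 0.76 SD | 3.3 |

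An interaction only as large as the detectable main effect (0.229 SD) would have power Φ(0.229/0.163 − 1.960) = 29% at 50% deployed and Φ(0.229/0.272 − 1.960) = 13% at 10%. Whether power is sufficient therefore depends on a prevalence and an interaction size that the documents do not give. The claim can be neither confirmed nor refuted.

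**Does the choice of coding matter?** Suppose, again by assumption, that 50% were ever deployed and 20% recently deployed, the second group lying within the first.

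- A moderation of 0.572 SD confined to the recently deployed has 80% power with the matching coding. Under ever/never coding it appears as 0.572 × 0.2/0.5 = 0.229 SD, with power Φ(0.229/0.163 − 1.960) = 29%.
- If the same 0.572 SD applies to everyone ever deployed, recent/not-recent coding sees 0.572 × (1 − 0.3/0.8) = 0.358 SD, with power Φ(0.358/0.204 − 1.960) = 42%.
- In general, if the true effect is set to give 80% matched power, mismatched power is Φ(2.802φ − 1.960), where φ = √(q(1−p)/(p(1−q))), q is the share recently deployed and p the share ever deployed. This gives 9% at q = 10%, p = 70%; 61% at q = 30%, p = 40%; and 80% when q = p.

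Over 10–30% recent within 30–70% ever, the result thus runs from 9% to no loss at all, according to invented prevalences. Matched power is 80% by construction, so this exercise cannot test the plan's claim.

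**False positives.** Testing both codings (correlation 0.5 in the 20%-within-50% example) would give about 9% false positives per outcome instead of 5%. That requires an analyst to run both and report either, which no section plans.

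**What the text already settles.** Aim 2 names the moderator, the treatment contrast and three outcome domains. Power Analyses names the model class for the aims. Moderation of a treatment effect in such a model is ordinarily the treatment-by-moderator term. The adjustment sentence sets covariates that every treatment comparison must carry; it does not exclude further terms. The missing visit or contrast is not peculiar to moderation, since the SAP names none for the primary aims either.

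**The case for a change.** The strongest case for a change has three parts. Moderator power is offered as a reason for N, so it should be checkable. The SAP sets itself a standard of planning analyses in advance, and aim 2's key variable falls short of it. And the remedy is cheap: a definition, a model sentence, and a figure or a deleted phrase, with at most one added questionnaire item.

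The facts in this case stand. No item, window or coding is given, and no number supports the claim. A reader cannot judge moderator power from this text, and a definition fixed before outcome data are seen would be tidier.

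The case does not show an error. The SAP ties its Type I error protection to the main study hypotheses, whereas this is a secondary aim whose verb is to examine. The first reason for N, possibly small differences between arms, stands without the moderator phrase. Reading deployment status as a baseline characteristic is the sensible default, because a moderator of a randomized effect is ordinarily fixed before randomization; the follow-up reading would need the plan to ask for it, and it does not. The background list is open-ended, so the absence of a named item does not show that the item is not collected. The text also points to hypotheses and retention strategies that it does not contain, and Power Analyses ends just after introducing its estimate, so absence here is weak evidence of absence from the trial's materials.

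**Conclusion.** The gap is real, but it is missing detail of a kind that a competent analyst fills in the usual way: a baseline deployment variable and its interaction with treatment in the stated mixed model. No rule in the plan leads to a wrong analysis, and nothing in the documents shows the power claim to be false. No change follows.

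On the assumptions listed (two-sided 0.05, 80% power, SD 1, binary moderator, one 12-month comparison), the 600 followed would detect an interaction of 0.46 SD at 50% deployed, rising to 0.76 SD at 10%, against 0.23 SD for the main effect. Repeated measures, baseline adjustment, or count and binary outcomes would alter these sizes. A moderation result from this trial should be read with that limited sensitivity in mind, but that is a matter of interpretation and not a fault in the plan. The power losses from mismatched codings and the raised false-positive rate rest on assumed prevalences and on conduct the plan does not describe, so they carry no weight in the conclusion.
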